9.5 Baseline assessment and laboratory tests

Information on subject's demographics, anthropometric measures and vital signs will be obtained. A detailed history taking of subject's current medical and past medical history along with full clinical examination. Blood sampling will be conducted. Ultrasound thyroid and ECG scheduled and ECHO if needed. UPT will be done prior to randomisation. Please refer to section 12 for more details.

9.6 Assessment of compliance

Adherence will be assessed at each visit during therapy by checking the subject diary card, 2 weekly count of sachets/ tablets from returned bottles. And this will be documented by a member of the study team.

9.7 Discontinuation and interruption of treatment

Participants will be advised to be compliant to study drug at all times and advised to take the missed dose as soon as they can remember and not to take a double dose to make up for missed doses.

9.8 Assessment of efficacy

• Primary efficacy endpoints are:

1. Proportion of subjects with normal thyroid hormone levels: defined as serum free T_4 or serum Free T_3 levels measured at 2 and 4 weeks after initiation of study treatment.

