Duration of treatment with study medication:

4 weeks

Criteria for evaluation:

- 1. Efficacy endpoint(s)
 - Primary endpoint
 - 1. Proportion of subjects with normal thyroid hormone levels (Defined

as serum free T_4 or serum free T_3 levels) measured at 2 and 4 weeks after initiation of study treatment.

- 2. Safety endpoints
 - Number of subjects with adverse effects during the intervention and follow up period (total duration 6 weeks)
 - Number of subjects with serious adverse events during intervention and follow up period (total duration 6 weeks)

Statistical methods:

- For primary objectives, all comparisons of means between treatment will be analysed using one-way ANOVA and all pairwise comparisons of proportions between treatments will be analysed using two-sided Z test. Analyses will be based on intention-to-treat and per protocol analysis.
- 2. For secondary objectives, all comparisons of means between treatment will be analysed using one-way ANOVA and all comparisons of proportions will be analysed using chi-square test of independence. Analyses will be based on safety set analysis.

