and hence decrease stimulation of the thyroid gland in Graves' disease¹⁴. Few case reports have documented its efficacy in situation where rapid control of hyperthyroidism is required. Ozawa in his case series documented that following oral administration of 30 mg daily dose of prednisolone with or without ATDs, both serum T_4 and T_3 concentrations decreased rapidly and reached euthyroidism within 2 weeks and subtotal thyroidectomies were performed uneventfully in all 4 cases¹⁷. Another study reported the addition of betamethasone 0.5mg 6 hourly, iopanoic acid 500 mg 6 hourly and propanolol 40 mg 8 hourly to 14 patients with hyperthyroidism submitted to subtotal thyroidectomy because ATDs have failed to control thyrotoxicosis and found that patients had normal T_3 levels by day 5 and T_4 reduction noted but has not reached normal levels by 5 days of treatment¹⁵. One study reported rapid normalization of thyroid function with prednisolone 20 mg daily as an adjunct when patients develop resistance to maximum treatment of carbimazole¹⁴. There were no reported serious side effects in the case series mentioned above.

Evidence in literature shows that adjunctive therapy such as cholestyramine and prednisolone may have a role to play in the management of hyperthyroidism. So far, studies on cholestyramine have proven its efficacy but they are small in size and have not been recommended in clinical guidelines. There are no clinical trials conducted in the asian population. A Cochrane systematic and current review is currently ongoing by Salazar et al. to asesss the efficacy of bile acid sequestrants as a standard adjunctive treatment therapy in hyperthyroidism and whether to recommend it in clinical practice guidelines¹⁸. This study would add weight to the ongoing systematic review. On the other hand, no clinical trials have been conducted to assess prednisolone as an adjunctive therapy to date and the safety profile unknown. We aim to compare the efficacy and safety profile of cholestyramine or prednisolone as adjunctive therapy to no adjunct. We also aim to compare the efficacy of cholestyramine and prednisolone as adjunctive therapy. We hypothesize that with the addition of cholestyramine or prednisolone to ATDs, we are able to achieve euthyroidism more effectively and rapidly compared to ATDs alone which may be useful in many crucial clinical situations described above.

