8.4.1 Inclusion criteria

- 1. Provision of written consent by subject or guardian.
- 2. Subject of either sex, more than 18 years of age
- 3. Subjects with moderate to severe overt hyperthyroidism (caused by Graves' disease).
 - Moderate to severe overt hyperthyroidism is defined as Free T₄>
 1.5 times upper limit of normal reference range and TSH below lower limit of reference range, who are either newly diagnosed or previously diagnosed and receiving ATDs currently.
 - •Graves disease is defined as hyperthyroidism coupled with clinical signs of symmetrical diffuse goiter, thyroid orbitopathy, or diffuse and vascular thyroid on ultrasound or positive TRAb antibody.
- 4. Female patients will either be
 - post-menopausal for > 2 years
 - Women of childbearing potential can be included if surgically sterile or using double contraception with at least one method being barrier contraception. Women of childbearing potential must have a negative pregnancy test at screening and at randomisation. Pregnancy tests will be repeated during each visit.

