11.1.5 Follow up visit (Visit 5, Week 6)

Safety assessment to monitor for adverse events, monitor for symptoms and signs of adrenal insufficiency and monitor for iatrogenic hypothyroidism.

- 1. Medical history taking
- 2. Perform physical examination including vital signs
- 3. Record any AE or SAE
- 4. Obtain blood sample (total of 6 ml of blood will be sampled). Thyroid function test will be sent to central lab (Gribbles laboratory) whereas the others will be sent to respective site's laboratory. (FT₄, FT₃, TSH, Blood urea and serum electrolytes/ FBS or RBS)

Study Activities Table

	Screening	Baseline Assessment and Randomisation	Treat	ment	Follow up
Visit	1	2	3	4	5
Timeline (wks)	-1	0	2	4	6
Procedures					
Informed consent	Х				
Check eligibility	х				
Blood sample for screening ^a	х				
Randomisation		X			
Patient demographics	Х				
Medical History	х				
Complete physical exam	х				
Height (cm), Weight (kg)	х	Х	х	Х	Х
Vital signs (BP, HR, Weight, Temp)	Х	X	Х	Х	Х
FT ₄ & FT ₃ & TSH	х	X (central lab)	X (central lab)	X (central lab)	X (central lab)
TRAb levels		X (central lab)			
FBS/ RBS	Х		Х	Х	Х
BUSE	Х		Х	Х	Х
UPT ^b	х	X	Х	Х	
U/S Thyroid		Х			
ECG		Х		Х	
ECHO ^c		X			
Efficacy assessment			Х	Х	
Concomitant medication			х	Х	
Report AE and SAE			Х	Х	Х
Dispense study treatment			х	Х	
Assess compliance			х	Х	
Complete relevant section of CRF			X	Х	Х

^a HepBsAg, Anti HCV ab, HIV1/2 ab, FBC, BUSE/Creatinine, LFT, FBS/RBS, FLP. Written consent will be taken for HIV test. All blood tests on screening visit including thyroid function test will be sent to the respective site's laboratory.

^b For women of childbearing age

^c Only if clinically suggestive of thyrotoxic cardiomyopathy or has atrial fibrillation

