11.3 Sample handling and analysis

11.3.1 Collection

The only biospecimen involved in this study is blood. Blood draws of 5-10 mls would be performed as stated in the study activities table and before the dose of study drug. Blood specimen will be taken by a dedicated nurse or doctor.

The blood tests for **screening visit** will be sent to the **respective site's own laboratory.** The tests are:

- Free T₃, Free T₄, TSH
- HepBsAg, Anti HCV ab, HIV1/2 ab
- Full Blood Count
- Renal function test

- Liver function test
- Fasting blood sugar/ Random blood sugar (FBS/RBS)
- Fasting lipid profile

Subsequent FBS/RBS, renal profile for study treatment visits and follow up visits will also be sent to the respective site laboratory. Screening thyroid function tests results will not be analysed and therefore would not require specimens to be sent to a central laboratory.

Free T_4 , Free T_3 , TSH and TRAb levels for baseline and randomisation visit, study treatment visits (Visit 3 Week 2 and Visit 4 Week 4) and follow up visit (Visit 5 Week 6) will be sent to the centralised laboratory (Gribbles Pathology Laboratory Central Headquarters) for processing.

Request form with the patient's particulars shall be duly filled at the hospital site. Specimen should be individually packed in a specimen carrier bag with the request form. A call should be made by Site coordinator to Gribbles Pathology Careline number ([name]) for specimen pick up. Gribbles courier will be dispatched for specimen collection. Specimen transport will be done using a cooler bag (cool transport). Specimens will be collected by courier from the hospital site.

After checking the specimen from the courier, the laboratory staff will proceed to process the sample. Specimens are centifuged prior to sending it for analysis. Once centrifugation is done, the blood specimen is sent to the central headquarters laboratory for analysis. After test has been done, results are reviewed and if needed, validated before release.

Pre and post counselling test would be offered for HIV test in line with general practice and if positive be notified as per Malaysian law. Specimens would not be stored for future research.

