11.4 Laboratory analysis

#	Test	Method
1	Free T ₄	1. Type of kit : SIEMENS HEALTHCARE
		DIAGNOSTIC (SIEMENS HEALTHINEERS)
		2. Name of analyser : CENTAUR Xp
		Type of sample: Serum (recommended)
		4. Methodology: Direct Chemiluminescence
		competitive immunoassay
		5. Measuring range : 1.3 - 155 pmol/L
		6. Imprecision (CVs) : This assay exhibits total
		imprecision of \leq 7.3% CV
		7. Reference ranges :
		Adult : 9-25 pmol/L
2	Free T ₃	1. Type of kit : SIEMENS HEALTHCARE
		DIAGNOSTIC (SIEMENS HEALTHINEERS)
		2. Name of analyser : CENTAUR Xp
		3. Type of sample : Serum (recommended)
		4. Methodology : Direct Chemiluminescence
		competitive immunoassay
		5. Measuring range : FT3 : 0.3 - 30.8 pmol/L
		6. Imprecision (CVs) :
		This assay exhibits total imprecision of $\leq 3.7\%$
		7. Reference ranges :
		Adult : 3-6.5 pmol/L

		1. Type of kit : Siemens Healthcare Diagnostic
3	тѕн	(Siemens Healthineers)
		2. Name of analyser : Centaur Xp
		3. Type of sample : Serum (recommended)
		4. Methodology : TSH: 3 RD Generation Antibody
		capture.
		5. Measuring range : 0.008 - 150 μIU/L
		6. Imprecision (CVs) :
		This assay exhibits total imprecision of $\leq 3.8\%$
		7. Reference ranges :
		Adult : 0.4-4.7 mU/L
		1. Type of kit : Euroimmun Anti TSH Receptor
4	TRAb levels	(TRAb) ELISA (IgG)
		2. Name of analyser : EUROANALYSER
		3. Type of sample : Serum only
		4. Methodology : ELISA
		5. Measuring range: 0.16 to 40 IU/ml
		6. Imprecision (CVs): Interassay variation
		(n=20) with mean of 18.57 IU/ml is CV of
		7.6%
		7. Reference ranges :
		Negative: <1.0 IU/ml
		Positive: >1.0 IU/ml
		8. Storing and packaging of sampling instructions
		and methods: Serum sample storage 2-8°C for
		up to 14 days

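### The primary endpoint names two hormones and two visits but no primary hormone, primary visit or success rule, leaving four undesignated primary results per treatment comparison

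*Combined protocol and SAP*

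**What the plan says.** - **Section 1 (Synopsis).** Under a singular heading for the primary endpoint, normal hormone levels are defined "as serum free T_4 or serum free T_3 levels) measured at 2 and 4 weeks after initiation of study treatment".
- **Section 9.8.** The lead-in is plural, "Primary efficacy endpoints are", but a single item follows, "defined as serum free T_4 or serum Free T_3 levels measured at 2 and 4 weeks after initiation of study treatment".
- **Section 13.1.** There are two calculations, each labelled as the primary objective: one for normal FT4 and one for normal FT3. Both use 80% power, a 30-point difference, a 40% control rate, a two-sided pooled Z test at 0.05, 41 per group, and 45 after 10% drop-out. Neither names a week. The 40% in the FT3 calculation is described as the rate of euthyroid status, not of normal FT3.
- **Section 11.1.5 (activities table).** Efficacy is assessed at both week 2 and week 4.
- **Section 13.2.2.** Pairwise Z tests are unadjusted for the multiple pairwise comparisons, and 13.1 justifies this for the three treatment groups. Neither section mentions hormones or visits. Under the primary objective, 13.2.2 also lists ANOVA of means and both intention-to-treat and per-protocol analyses, without saying which leads.
- **Section 11.4.** Central-laboratory ranges are given, for FT4 "Adult : 9-25 pmol/L" and for FT3 3 to 6.5 pmol/L. Normal is therefore definable for each hormone.

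**The concern.** The trial's hypothesis in Section 6 is that with an adjunct "we are able to achieve euthyroidism more effectively and rapidly compared to ATDs alone". The plan does not say which result would confirm it. Two analysts following the protocol faithfully could report different primary results from the same data: FT4 or FT3, week 2 or week 4, either, or all. Treatment is open label, and the choice could be made after the results are known.

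A secondary difficulty is the word *or*. Taken literally, one normal hormone is enough, so a patient with the other still raised would be a success. Section 6 reports a guideline definition of overt hyperthyroidism as raised FT4 and/or total T3 with low TSH. A literal success could therefore still have the disease.

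**Working it through.** **Inputs.** From 13.1: 40% vs 70% (40% plus 30 points), two-sided pooled Z test, alpha 0.05, 41 evaluable and 45 randomised per arm. Assumed: the correlation r between outcomes in the same patient, on an underlying normal scale, is 0.9 to 0.5, with 0 as an outer bound.

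**1. The plan's own figure.** n = [1.960·√(2·0.55·0.45) + 0.842·√(0.4·0.6 + 0.7·0.3)]² / 0.3² = 41.97. Exact enumeration of the pooled Z test gives power of 79.6% at 40, 81.3% at 41 and 81.8% at 45 per arm. So 41 is right for one endpoint, and 41 × 1.1 = 45.1 agrees with 45.

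**2. Count.** 2 hormones × 2 visits = 4 results per treatment comparison.

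**3. If any one of the four counts.** With independent tests the risk is 1 − 0.95⁴ = 18.5%. Simulation used 40,000 trials per value of r, 45 per arm, 40% in both arms, and four equally correlated outcomes:

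| r | At least one p<0.05 |
|---|---|
| 0 | 17.9% |
| 0.5 | 16.8% |
| 0.9 | 12.7% |

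With 40% normal on each, both are normal in 23.9% of patients at r = 0.5 and 33.1% at r = 0.9. The correlation of the yes/no outcomes is then (0.239 − 0.16)/0.24 = 0.33 and (0.331 − 0.16)/0.24 = 0.71. Setting the correlation directly on the test statistics agrees: 17.4% at 0.3 and 13.0% at 0.7. It falls to 9.4% only at 0.9 on that scale.

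**4. If both hormone tests must succeed at one visit.** Suppose each hormone moves from 40% to 70%, with 45 per arm:

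| r | False-positive risk | Power |
|---|---|---|
| 0 | 0.2% | 67.1% |
| 0.5 | 0.6% | 69.6% |
| 0.9 | 1.6% | 73.7% |

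As a check at r = 0, 0.818² = 0.669.

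**5. Literal *or*.** With 40% normal on each hormone, the control success rate would be 46.9% (r = 0.9), 56.1% (0.5) or 64.0% (0), not 40%. At r = 0.5 the share of control successes with one hormone out of range is (0.561 − 0.239)/0.561 = 57%. It is 30% at r = 0.9 and 75% at r = 0.

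**6. A both-normal responder.** If each hormone moves from 40% to 70%, the responder rates are 33.1% vs 63.8% (r = 0.9) or 23.9% vs 55.7% (r = 0.5), with power of 83% to 88% at 45 per arm. If the second hormone moves only to 55%, power is 48% to 60%. If it does not move, power is 10% to 21%.

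**The case against.** The best defence is that 13.1 settles the reading. It plans two separate hormone endpoints, each with its own Z test, and nothing there implements an either-hormone responder; *or* may simply list the two hormones. The plan is also open about not adjusting, the sample size reproduces, and no passage says that any single significant result will be called success. Much of this stands. The two-endpoint reading is the better supported one, so the literal *or* is only a secondary point. It does not remove the main gap. Two endpoints at two visits still have no hierarchy or success rule, and the waiver of adjustment does not extend to them.

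A reader might infer more than the documents support:

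- **Much larger error rates**, from pooling all three arm comparisons, both analysis sets and ANOVAs of hormone means. Section 13.1 openly treats the arm comparisons as separate trials. No passage makes the per-protocol set a separate route to success or names an FT4 or FT3 mean as an endpoint.
- **A conflict over the analysis set in 13.2.** Its sentence on intention-to-treat breaks off, so nothing can be built on it.
- **That a patient still at the entry level of FT4 would demonstrably be a success.** Entry requires FT4 above "1.5 times upper limit of normal reference range and TSH below lower limit of reference range". It is judged at screening, where "All blood tests on screening visit including thyroid function test will be sent to the respective site's laboratory", and 11.3.1 adds "Screening thyroid function tests results will not be analysed". The site ranges are not given, so entry values cannot be matched to the central range.
- **That one arm would gain.** The documents do not show this.

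**Conclusion.** The point holds and should be fixed before analysis. Each treatment comparison has four primary results without a designated hormone, a designated visit or a success rule. The consequence depends on the rule eventually applied. If any one counts, the false-positive risk is about 13% to 17% per comparison (18% at zero correlation) against a nominal 5%. If both hormone tests must succeed at one visit, error stays at or below about 2%, but power is about 67% to 74% instead of 80%. Both ranges rest on assumed correlations, and the first also rests on a rule that the plan neither states nor excludes. The sample size itself is not in error: 41 evaluable per arm is correct for one hormone at one visit.

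**What to change.** 1. In Sections 1, 9.8, 13.1 and 13.2.2, name in identical words one primary hormone, normal meaning within its central-laboratory range in 11.4, and one primary visit. Make the other hormone and the other visit secondary.
2. In 13.1, state which hormone and week the 40% vs 70% describes. The 45 per arm then stands: 82% power at 45 and 81% at 41.
3. If the sponsor wants both hormones primary, there are two ways. One is to require both tests to succeed at the named visit and restate power as about 67% to 74%. The other is to define a both-normal responder and redo 13.1 for that composite, whose power depends heavily on how far the second hormone moves (step 6 of the working).
4. In 13.2.2, name intention-to-treat as the primary set with per-protocol supportive, and make any ANOVA of means secondary.

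The cost is wording. FT4 and FT3 are already measured centrally at weeks 2 and 4, so no new data are needed. The price is that one hormone and one visit lose primary status.

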9.9 Assessment of safety

Safety data will be analysed for the data collected throughout intervention period and up to follow up period. The following endpoints will be collected:

- Number of subjects with adverse effects during the intervention period and follow up period (total duration 6 weeks)
 - Subjects will be asked to report about adverse reactions (specified in the protocol) at 2 weeks, 4 weeks of intervention period and 2 weeks after end of study treatment period.
 - Number of subjects with serious adverse events during intervention period and follow up period (total duration 6 weeks)
 - Subjects will be asked to report about SAE immediately during the intervention period and follow up period

Safety and tolerability assessments will consist of:

- Regular performance of physical examinations
 - 1. BP, PR, Temperature, Weight (kg)
- Regular monitoring of laboratory tests
 - FPG/ RPG, Electrolytes (Na⁺, K⁺, Urea, Creatinine), FT₄, FT₃, TSH
- Monitoring and recording all adverse reactions and serious adverse events

